6.2 Secondary Endpoints

Secondary endpoints will include the following:

- The changes in Police Interaction Knowledge Questionnaire Scores from Pre-Treatment to Post-Treatment for the Virtual Reality Intervention and BE SAFE Video-Based intervention or treatment-as-usual:
- The maintenance of learned skill improvements, indexed via the 4-week (Cycle B) Follow-Up administration of the Virtual Police Interaction Assessment.

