6.3.2 Efficacy Analysis

The primary analysis will be based on an intention to treat approach and will include all subjects randomized at Visit 1.

The primary efficacy endpoint will be the change in post-treatment Live Police Interaction Assessment Scores between the Virtual Reality Intervention and BE SAFE Video-Based intervention and the change in scores between the Baseline Assessment and Live Police Interaction Assessment. In the case of Cycle 2, the Baseline Assessment will be compared to the Virtual Police Interaction Assessment between the Virtual Reality Intervention and treatment-asusual groups. The study hypothesis is that participants randomly assigned to the Virtual Reality Intervention will perform better on the post-treatment Live or Virtual Police Interaction Assessment than will participants randomly assigned to the BE SAFE Video-Based intervention or treatment-as-usual condition.

The secondary endpoint will include changes in Police Interaction Knowledge Questionnaire Scores from Pre-Treatment to Post-Treatment for the Virtual Reality Intervention and BE SAFE Video-Based intervention or treatment-as-usual. The study hypothesis is that participants randomly assigned to the Virtual Reality Intervention will exhibit significantly greater improvement from Pre-Treatment to Post-Treatment on Police Interaction Knowledge Questionnaire than will participants randomly assigned to the BE SAFE Video-Based intervention condition or the treatment-as-usual condition. An additional Secondary endpoint is maintenance of learned skill improvements, indexed via the 4-week Follow-Up administration of the Virtual Police Interaction Assessment in Cycle B. The study hypothesis is that participants randomly assigned to the Virtual Reality Intervention will exhibit significantly greater Live Police Interaction Assessment Scores and skill improvement/maintenance 4-week follow-up than will participants randomly assigned to the treatment-as-usual condition.

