6.4 Sample Size and Power

This study will compare the PSM VR intervention to treatment-as-usual (TAU) in a total of 96 adolescents and adults with ASD, in two separate studies (i.e., n=48 per study). The most relevant study to date (Didehbani, Allen, Kandalaft, Krawczyk, & Chapman, 2016) included 30 7-16 year-olds with ASD in a pre/post virtual reality intervention to improve social cognitive skills. This study suggested a medium-to-large within-group effect of VR intervention on emotion recognition (Cohen's d = .63), but did not compare two interventions. Sensitivity analysis using G*Power indicated that intervention differences using our proposed sample size (N=48 per group) will be detected with a critical t of 1.99, and that we will be able to detect differences with effect sizes of Cohen's d = .74 or larger. Data will be behaviorally coded from video interactions and correct answers marked on knowledge tests. Scores will be summed, averaged, and examined for normality at the group level. Normally distributed data will be analyzed using parametric statistics (e.g., ANOVA, regression, Pearson correlation), and data that do not meet normality assumptions will either be transformed or will be analyzed using nonparametric statistical tests (e.g., Chi-square, Spearman correlation). Analyses will be corrected for comparisons. To compare PSM to BE SAFE, an Analysis of Variance (ANOVA) with Group (PSM VR Intervention, BE SAFE The Movie Video Modeling Intervention) as a Between-Subjects factor will be conducted for Live Interaction data. A separate ANOVA (or comparable statistical test) will be conducted for Questionnaire data. Relevant potential covariates include knowledge of police interactions at intake, sensory sensitivity scores, verbal abilities, and chronological age.

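### Free improvement: section 6.4 leaves the model for the knowledge endpoint open; always adjusting for the pre-treatment score would close the choice and be more precise than analysing change

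*Combined protocol and SAP*

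**What the plan says.** Section 6.2 lists as a secondary endpoint "The changes in Police Interaction Knowledge Questionnaire Scores from Pre-Treatment to Post-Treatment", for the VR arm and its comparator. Section 6.3.2 repeats this and gives the hypothesis that VR participants "will exhibit significantly greater improvement from Pre-Treatment to Post-Treatment on Police Interaction Knowledge Questionnaire" than controls. Section 5.4.3 has the questionnaire given to every participant before and after treatment, and again at follow-up in Cycle B.

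Section 6.4 is the only place that names a test for this endpoint: "A separate ANOVA (or comparable statistical test) will be conducted for Questionnaire data". The sentence gives no factors and no form of the outcome. The sentence before it names Group "as a Between-Subjects factor will be conducted for Live Interaction data", which is a different outcome. Section 6.4 then says: "Relevant potential covariates include knowledge of police interactions at intake", together with sensory sensitivity, verbal ability and age.

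Section 6.3.1 adds a rule for both primary and secondary analyses: baseline characteristics that differ significantly between arms become covariates. Section 9.1.1 has a similar rule for the primary analyses. Nowhere does the plan commit to adjusting for pre-treatment knowledge in every case.

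**The concern.** The plan defines the endpoint but not the model. Two things follow.

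The first is precision. The most natural reading, a comparison of change scores, is valid under randomisation. It is less precise than comparing post-treatment scores adjusted for the pre-treatment score, and that score is already collected from everyone.

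The second is freedom of choice. Whether intake knowledge enters the model can depend on a baseline significance test or on a decision made at analysis. Such a choice can be made with the outcome data in view. The endpoint is secondary, but the abstract names the police knowledge assessment as one of the two main outcome measures.

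**Working it through.** **The plan's own figure.** Section 6.4 gives a detectable effect of d = 0.74 with a critical t of 1.99. It states neither alpha nor power. With 48 per group, two-sided 5% and 95% power, the noncentral t gives a critical t of 1.986 and d = 0.743, so the figure reproduces under those assumptions. It uses 48 per group, whereas the same section plans 48 per study. That is a separate matter, and nothing below depends on it.

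**Inputs.** There are 48 participants per study (6.4). The allocation ratio is not stated, so I assume 1:1 and n = 24 per arm. I also assume two-sided 5% and an equal SD before and after treatment. The pre-post correlation ρ is not in the documents, so 0.3, 0.5 and 0.7 are shown.

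**Formula.** In SD units, the standard error of the arm difference is k·√(2/n), where:
- change score: k = √(2(1−ρ))
- ANCOVA on the pre-score: k = √(1−ρ²), with 45 rather than 46 degrees of freedom
- post score only: k = 1

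The ratio of the change SE to the ANCOVA SE is √(2/(1+ρ)). It exceeds 1 for every ρ below 1.

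**Detectable difference.** With k = 1 and 24 per arm, the difference detectable at 80% power is 0.826 SD. The other values are 0.826 × k, to the accuracy shown. For example, at ρ = 0.3 change gives 0.826 × 1.183 = 0.98 and ANCOVA gives 0.826 × 0.954 = 0.79.

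**Power at a true difference of 0.6 SD.** The noncentrality is 0.6 × √12 / k = 2.078/k. At ρ = 0.3 this is 1.757 for change and 2.179 for ANCOVA.

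| ρ | k, change | k, ANCOVA | SE ratio | Detectable difference, change / ANCOVA | Power at 0.6 SD, change / ANCOVA |
|---|---|---|---|---|---|
| 0.3 | 1.183 | 0.954 | 1.24 | 0.98 / 0.79 | 41% / 57% |
| 0.5 | 1.000 | 0.866 | 1.15 | 0.83 / 0.72 | 53% / 65% |
| 0.7 | 0.775 | 0.714 | 1.08 | 0.64 / 0.59 | 75% / 81% |

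In sample size, the variance ratio 2/(1+ρ) is 1.54, 1.33 and 1.18. The change analysis would therefore need about 54%, 33% and 18% more participants to match the precision of ANCOVA.

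**Disagreement between the two tests.** In simulated trials with normal scores, 24 per arm and a true difference of 0.6 SD, change and ANCOVA disagree on significance in about 24%, 19% and 11% of trials at ρ = 0.3, 0.5 and 0.7.

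**Cost of an open choice.** With no true effect, each of the three analyses alone has a 5% error rate. If whichever of post-only, change and ANCOVA is significant can be reported, the simulated false-positive rate is about 9% to 10%.

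**The case against.** The strongest objection is that nothing here is contradictory. A reader might infer that 6.4 prescribes an ANOVA on Group alone for the questionnaire, in conflict with the change endpoint in 6.2 and 6.3.2. The text does not support that. The Group factor is written for the live interaction data, and the questionnaire sentence leaves the model open. An ANOVA of change by group satisfies 6.2, 6.3.2 and 6.4 together. So does a Group-by-Time ANOVA, which with two time points gives the same test of the arm difference. This part of the objection stands: the issue is under-specification.

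It also limits which numbers matter. Post-only and change analyses disagree on significance in about 32%, 34% and 39% of simulated trials at the three correlations. But post-only drops the endpoint as defined, so that is not the fair comparison. Change against ANCOVA is, and its disagreement is smaller. The 9% to 10% error rate likewise counts post-only among the options, and it would be lower if only change and ANCOVA were in play.

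It can also be said that analysing change is legitimate and that the gain is modest when ρ is high. Both are true: at ρ = 0.7 the SE ratio is only 1.08. Even so, ANCOVA has the smaller standard error at every correlation shown, and the pre-score is already collected.

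Finally, 6.3.1 does say when a baseline variable enters a secondary analysis. That rule makes the model depend on a significance test in the observed data, so it does not settle the choice in advance.

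**Conclusion.** The point holds as a free improvement to a secondary endpoint, not as an error or a contradiction. Section 6.4 does not fix the form of the outcome or the role of pre-treatment knowledge. The natural change-score reading has a standard error 8% to 24% larger than ANCOVA over ρ from 0.7 down to 0.3. At a true difference of 0.6 SD, that costs 6 to 16 percentage points of power (81% − 75% and 57% − 41%).

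These sizes rest on 1:1 allocation with 24 per arm, equal variances, two-sided 5% and an assumed range for ρ. The direction does not depend on the value of ρ within that range. The inflation to about 9% to 10% is what the openness would allow if all three analyses were treated as available. The documents do not show that anyone intends to use it that way.

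**What to change.** In 6.4, with 6.2 and 6.3.2 aligned, prespecify one analysis of the knowledge endpoint for each cycle: an ANCOVA of the post-treatment knowledge score on arm (VR against BE SAFE in Cycle A, VR against treatment-as-usual in Cycle B), with the pre-treatment score always included. Three details should be written down:

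- The covariate is the pre-treatment score on the same questionnaire, the one in 5.4.3. State that this is what 6.4 means by knowledge at intake for this endpoint, and take it off the list of potential covariates here. This needs saying because 5.1.5 describes a Police Knowledge Assessment of prior experience with and feelings about police, 5.4.3 describes a Police Knowledge Questionnaire on officer expectations, and 4.3 uses the Assessment name for the pre and post measure.
- The significance-triggered covariate rule in 6.3.1 does not alter this model.
- Raw pre-to-post change is reported by arm, descriptively.

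Under randomisation this model estimates the same arm difference as the change analysis, so it still answers the greater-improvement hypothesis. The cost is SAP wording and one degree of freedom, with no new data or visits.

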6 STATISTICAL CONSIDERATIONS

6.1 Primary Endpoints

The primary efficacy endpoints will be the change in post-treatment Live and Virtual Police Interaction Assessment Scores between the Virtual Reality Intervention and treatment-as-usual groups, and the change in scores between the Baseline Assessment and Virtual Police Interaction Assessment.

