6.3 Statistical Methods

6.3.1 Baseline Data

Baseline and demographic characteristics will be summarized by standard descriptive summaries (e.g., means and standard deviations for continuous variables such as age and percentages for categorical variables such as gender). Statistical analyses will be conducted to compare groups on each of the measures. Any baseline characteristics which exhibit statistically significant group differences despite stratified random assignment will be utilized as co-variates in both Primary and Secondary statistical analyses of intervention effects.

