9 STUDY ADMINISTRATION

9.1 Treatment Assignment Methods

9.1.1 Randomization

We will employ stratified random assignment using variables including developmental age and sex. Other participant variables that differ between our groups following this stratified randomized assignment will be accounted for statistically during our primary analyses.

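### The baseline police-interaction score is collected from everyone but not prespecified as a covariate; whether it is adjusted for depends on the imbalance observed

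*Combined protocol and SAP*

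**What the plan says.** Sections 5.4.1.1 and 5.4.1.2 have all participants complete a Baseline Assessment of police-interaction skill before their first session: a role play with a staff member in Cycle A, a remote VR assessment in Cycle B.

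**Model.** For Cycle A, section 6.4 plans an ANOVA with Group "as a Between-Subjects factor will be conducted for Live Interaction data". It then adds: "Relevant potential covariates include knowledge of police interactions at intake, sensory sensitivity scores, verbal abilities, and chronological age". The knowledge item in that list is a questionnaire measure, not the interaction score. For Cycle B, section 6.3.2 says only that "the Baseline Assessment will be compared to the Virtual Police Interaction Assessment between the Virtual Reality Intervention" and treatment-as-usual arms. The model there falls under the generic parametric-or-nonparametric wording of 6.4.

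**Endpoint.** The baseline score enters the primary endpoint as a change: "the change in scores between the Baseline Assessment and Live Police Interaction Assessment" (6.3.2, Cycle A) and "the change in scores between the Baseline Assessment and Virtual Police Interaction Assessment" (6.1). The 6.3.2 hypothesis, however, is that VR participants "will perform better on the post-treatment Live or Virtual Police Interaction Assessment".

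**Adjustment rules.**
- 6.3.1: "Any baseline characteristics which exhibit statistically significant group differences despite stratified random assignment will be utilized as co-variates", in primary and secondary analyses. No significance level is given.
- 9.1.1: "Other participant variables that differ between our groups following this stratified randomized assignment will be accounted for statistically during our primary analyses". No threshold is given.
- 5.1.5, for the demographic and medical history form: those data become covariates if the groups turn out unbalanced on important features.

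**The concern.** A baseline measurement of the outcome construct is usually the strongest covariate available, and here it costs nothing extra to collect. The plan permits adjusting for it but never commits to doing so. Three analyses of the same data stay open: post-treatment score alone, between-arm change, and post-treatment score adjusted for baseline. Which of the first two is better depends on a correlation nobody knows yet. ANCOVA avoids that guess.

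The imbalance rules do not close the gap. They make the form of the primary model depend on the baseline data observed, and a significance test at baseline seldom fires in a randomized trial. What is at stake is precision in two small studies, and a primary model settled before outcomes are seen.

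**Working it through.** **Inputs.** Section 6.4 gives 48 per study and, for its sensitivity calculation, 48 per group; d = 0.74; critical t = 1.99. Assumptions: 1:1 allocation (so 24 per arm from 48 per study), equal SDs, bivariate normal scores, two-sided 0.05, and 0.05 as the level for the 6.3.1 rule. The baseline-to-post correlation r is not in the documents; 0.3/0.5/0.7 is shown.

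**The plan's own figure.** For a two-sample t-test with 48 per group, df = 94 and critical t = 1.986. The detectable d is 0.578, 0.669 and 0.743 at 80%, 90% and 95% power. So 0.74 and 1.99 reproduce at 48 per group with 95% power. That power is inferred; the plan states none.

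**Formulas at n = 24 per arm, d = 0.74.**
- Post-only: noncentrality 0.74/√(2/24) = 0.74/0.2887 = 2.563, df 46, critical t 2.013.
- Between-arm change: standardized effect 0.74/√(2(1−r)) = 0.625/0.740/0.955, df 46.
- ANCOVA: standardized effect 0.74/√(1−r²) = 0.776/0.854/1.036, df 45. The variance term is 2/n + D²/Sxx, with D the chance baseline difference between arms and Sxx the pooled within-arm sum of squares; power is averaged over D.
- Trigger rule: 200,000 simulated trials per setting; ANCOVA if the baseline difference has p < 0.05, otherwise the default test.

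| Power, 24 per arm | r = 0.3 | r = 0.5 | r = 0.7 |
|---|---|---|---|
| Post-only | 0.709 | 0.709 | 0.709 |
| Post-only with 6.3.1 trigger | 0.709 | 0.716 | 0.728 |
| Between-arm change | 0.564 | 0.709 | 0.900 |
| Change with 6.3.1 trigger | 0.573 | 0.716 | 0.904 |
| ANCOVA in every trial | 0.739 | 0.817 | 0.935 |

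The ANCOVA gain over post-only is 0.739 − 0.709, 0.817 − 0.709 and 0.935 − 0.709: about 3/11/23 points. Over change it is 17.5/10.8/3.5 points.

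**Why the trigger recovers so little.** It fires in about 5% of trials. A baseline difference of up to 2.013 × 0.2887 = 0.58 SD leaves the model unadjusted.

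**Type I error under the 6.3.1 trigger.** 0.047/0.044/0.037 with a post-only default and 0.041/0.043/0.046 with a change default. There is no inflation.

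**Low r.** At r = 0, 0.1 and 0.2, ANCOVA power is 0.699, 0.703 and 0.716 against 0.709 post-only. Break-even is r = 0.151, or 0.157 with two uninformative stratification terms added.

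**48 per arm.** Post-only 0.948; change 0.858/0.948/0.996; ANCOVA 0.962/0.985/0.999. The gain is about 1/4/5 points over post-only and 10/4/0.3 over change. Break-even against post-only is about r = 0.11.

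**The case against.** **The baseline is already used.** Sections 6.1 and 6.3.2 bring it in through change, and a between-arm change score is a valid randomized comparison. That stands: preferring ANCOVA is an argument about precision, not validity. But change had lower power at 24 per arm for every r checked from 0 to 0.8, and in Cycle A it subtracts a staff role play from an encounter with an officer (5.4.2.1).

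**The gain may be small.** This also stands. The two different assessments make a low r plausible in Cycle A, and the 23-point figure needs r = 0.7. The sample size is itself contradictory within 6.4; at 48 per group post-only power is already about 95%.

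**The rules may be one rule.** Section 9.1.1 may only paraphrase 6.3.1. A reader might infer a sharp conflict, since a reading of 9.1.1 as imbalance above 0.25 SD would fire in about 39% of trials against 5%. That cut-off appears nowhere in the documents, so the contrast only illustrates how open the wording is.

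**A false-positive problem?** A reader might infer that the open model inflates type I error. If the better of post-only and ANCOVA were picked after the fact, the rate would be 6.5/7.1/8.2%, and 9.2/9.5/10.0% with change as a third option. Nothing in the documents says results would be picked that way, and the significance rule as written is slightly conservative. These figures are an outer bound, not a finding.

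**Non-normal data.** Section 6.4 allows transformation or nonparametric tests; the power figures here assume normality.

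**Conclusion.** The point holds as a matter of precision and prespecification. No section commits to the baseline interaction score as a covariate in either cycle, and whether it enters the primary model depends on observed imbalance. The unadjusted comparison remains valid.

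The size depends on two things the documents do not settle. If 48 per study means 24 per arm, prespecified ANCOVA is worth about 3 to 23 points of power over post-only as r runs from 0.3 to 0.7, and about 18 down to 3 points over a change score. If there are 48 per arm, the gain is a few points, apart from about 10 over change at r = 0.3. With r below about 0.15 at 24 per arm there is no gain over post-only, and at most about 1 point is lost. The need for one fixed model is the same in every case. The change is worth making because the data are already being collected.

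**What to change.** - In 6.3.2 and 6.4, prespecify one primary between-arm analysis for each cycle: an ANCOVA of the Visit 3 Police Interaction Assessment score on arm, Baseline Assessment score and the stratification factors used in randomization. Include all terms whatever the baseline tests show.
- State that the Baseline Assessment is done before randomization, or before the participant's allocation is known. Section 4.2 lists randomization under characterization visits and 4.3 lists the Baseline Assessment under intervention visits; 5.4.1 places it only before the first session, so the order is unclear.
- In 5.1.5, 6.3.1 and 9.1.1, limit imbalance-triggered adjustment to sensitivity analyses.
- Keep the between-arm baseline-to-post change of 6.1 and 6.3.2 as a supportive analysis. Say openly that the ANCOVA replaces it as the primary test, since this alters the stated primary endpoint, and that any within-arm change is not a randomized comparison.

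**Cost.** Wording and a few degrees of freedom, with no new data. If r is near 0, power at 24 per arm falls by about 1 point against post-only (70.9% to 69.8% with two stratification terms).

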7 STUDY INTERVENTION

7.1 Virtual Reality Intervention

Floreo's Police Safety Module (PSM) will offer a supervised VR experience for individuals with ASD. The software will be a downloadable application that provides a three-dimensional immersive scene for headset-compatible smartphones and a supervisory overview that can run on smartphones or tablets. The individual with ASD will use a smartphone capable of running the application with a dedicated headset providing the virtual environment.

- 1. Immersive story-based intervention. Floreo's PSM provides a fully realized and intricately detailed urban environment (Appendix figure 1), designed to engage the user in a virtual encounter with law enforcement officers. The immersive VR environment engages the individual with ASD as an actor in a virtual narrative, incorporating strategies from both story-based intervention and video modeling. The opportunity to enter a virtual environment is likely to be appealing for adolescents with ASD. A law enforcement officer with extensive experience working with individuals with autism spectrum disorder along with members of the Philadelphia Police Department have provided ongoing input into content and environment design for this product.
- 2. *Video modeling*. Floreo's PSM provides video modeling to an individual with ASD. The video demonstrates the approach and initial engagement efforts of various police officers in the virtual environment, from the perspective of the individual wearing the HMD (Appendix figure 2).
- 3. Supervised Learning Environment. Floreo's PSM allows a monitor to use a tablet or phone to supervise the individual's virtual world. The devices used by individual with ASD and the monitor are communicatively paired together over a network connection (Appendix figure 3).

